Removed for public posting

SECTION VII: PROTOCOL DESCRIPTION

WHAT IS THE PURPOSE OF THE STUDY?

The purpose of this study is to determine the efficacy of a Mindfulness-based Intervention for Tics (MBIT) as compared to online psychoeducation, relaxation, and supportive therapy (dubbed Tic Information and Coping Strategies or TICS) in 48 adults with tic disorders.

We hypothesize that MBIT will result in significantly greater improvements in tic severity and tic-related impairment than TICS.

HOW WILL THE INFORMATION COLLECTED IN THE STUDY BE USED (examples: independent study, honors project, publication)

The results of this study may be presented at scientific conferences and/or published in the scientific literature. De-identified data from this study may also be combined with de-identified information from other research studies to answer additional research questions.

WHAT QUESTIONS WILL BE ANSWERED?

How efficacious is MBIT when compared to TICS for adults with tic disorders?

DESCRIPTION OF HUMAN SUBJECT POPULATION, TIME INVOLVEMENT & CONFIDENTIALITY

Participants

We aim to recruit 48 adults to participate in this study. To be eligible for participation, these individuals must:

- 1) be 18 years of age or older,
- 2) possess a primary diagnosis of Tourette Syndrome or Persistent Tic Disorder,
- 3) be fluent in English

- 4) reside in the United States,
- 5) either not be taking any tic suppressant medication or other psychotropic medication or be at a stable dose for 8 weeks prior to the baseline assessment and throughout the study

And must NOT:

- 1) be receiving concurrent psychotherapy for the duration of the study
- 2) have prior extensive experience with mindfulness and/or meditation and
- 3) have another medical or psychological condition that would prevent the individual from fully engaging in the study or require a higher level of care (e.g., suicidality).

Recruitment & Selection

We will recruit participants via online postings on the Bowdoin College website, the Massachusetts General Hospital website and facebook page, the Tourette Association of America (TAA) website and, with permission, the websites of other Tourette Syndrome Research or Clinical Centers in the US. We will also contact our colleagues in the field as well as state and local TAA chapters and support groups by email to inform them of the study. All recruitment materials are attached for review.

Time Involvement

Participants will complete the study in approximately 9 months. During this time, each participant will spend approximately 6 hours completing formal assessments (2 hours for the screening visit, 1 hour each for the baseline, post-treatment, 1-month and 6-month follow-up assessments) and approximately 6 hours per week for 8 weeks completing the intervention and self-report questionnaires.

Payment

Participants will be compensated a total of \$200 each (\$10/week for the weekly self-report questionnaires, \$30 each for the baseline, post-treatment, one-month and 6-month follow-up assessments).

Type of Involvement

Interested participants will complete a brief phone interview (see attached) with [name] to determine provisional eligibility. Potentially eligible participants will then be scheduled to complete informed consent with the PI via phone or videoconference and a formal screening assessment with the Independent Evaluator (IE; [name] @ MGH) via videoconference. After screening, eligible participants will be randomly assigned to one of the two interventions: online mindfulness-based tic reduction or online psychoeducation, relaxation, and supportive therapy. Once we have enough eligible participants to form a group (approximately 6-8 participants), we will schedule baseline assessments via videoconference with the IE for the week prior to the initiation of the intervention. Both interventions will last 8 weeks and consist of eight weekly 90-minute therapist-facilitated group videoconferences. Approximately one week, one months, and 6 months after completion of the intervention, participants will complete a follow-up assessment with the IE via videoconference.

Please see the attached protocol schema for a concise overview of the study procedures.

Interventions

Mindfulness-based Intervention for Tics (MBIT)

Mindfulness-based interventions typically involve three components: mindfulness practice (e.g., meditation, mindful movement), psychoeducation, and inquiry (i.e., group discussion of the practice and the application of the practice to one's life). In this online adaptation we will offer the intervention in eight weekly 90-minute therapist-facilitated group videoconferences. The PI or [name] will facilitate the weekly videoconferences. All participants will also be asked to complete approximately 30 minutes/day 4-6x/week of home practice.

Tic Information and Coping Strategies (TICS)

The TICS condition will mirror the mindfulness-based tic reduction condition in format and duration. In the video conferences, participants will be encouraged to discuss a weekly topic (e.g., causes of tics, talking to others about your tics, how tics affect your relationships) or skill (e.g., relaxation, communication) and provide social support to one another. Formal home practice will not be assigned. The PI or [name] will facilitate these conversations.

Assessment

Table 1. Schedule of Assessments

Measures	Screening	Baseline (Week 0)	Weeks 1- 8	Week 9	Week 13	Week 35
SCID	X					
YGTSS	X	X		X	X	X
CGI-S	X	X		X	X	X
CGI-I				X	X	X
TTHQ	X					
ATQ		X		X	X	X
PUTS		X	X	X	X	X
YBOCS		X		X	X	X
ADHD-RS		X		X	X	X
PHQ-9		X		X	X	X
DASS		X		X	X	X
WSAS		X		X	X	X
FFMQ		X	X ^a	X	X	X
CEQ			X ^b			
PSQ				X		
SCS		X		X	X	X
ARI		X		X	X	X
BITe		X		X	X	X
Tic Rating Form			X			
Problem Rating Form			X			
Homework Adherence Form			X ^c	X		
Adverse Event Monitoring Form			X	X		

Treatment Questionnaire					X	X
-------------------------	--	--	--	--	---	---

^aThe FFMQ will only be administered at week 4.

^bThe CEQ will be administered only after week 3 of the intervention.

^cThe Homework Adherence Form will only be administered to participants in the MBIT condition because they are the only ones who will receive formal home practice assignments.

Structured Clinical Interview for DSM-5 (SCID). The SCID is the gold-standard in semi-structured diagnostic interviews to establish DSM-5 diagnoses (First, Williams, Karg, & Spitzer, 2015). We will administer the SCID at screening to assess for the presence of current or past DSM-5 disorders.

Yale Global Tic Severity Scale (YGTSS). The YGTSS is the gold-standard clinician-rated instrument for assessing tic severity (Leckman et al., 1989). It has demonstrated excellent internal consistency, inter-rater reliability, and convergent and divergent validity (Leckman et al., 1989). The total tic score will serve as the primary outcome measure because it has demonstrated the greatest sensitivity to change in tic severity over brief periods of time (Lin et al., 2002).

Clinical Global Impression-Severity (CGI-S) and Clinical Global Impression-Improvement (CGI-I) Scales. The CGI-S and CGI-I are well-established clinician-rated measures of severity and improvement (Guy et al., 1976). Consistent with other treatment outcome studies in TS and CTD (e.g., Piacentini et al., 2010), we will define treatment responders as those who receive a rating of 'Very Much Improved' or 'Much Improved' on the CGI-I.

Tic Treatment History Questionnaire (TTHQ). This is a clinician-rated questionnaire assessing past and current treatments.

Adult Tic Questionnaire (ATQ). The ATQ (Abramovitch, [name], Woods, Peterson, Deckersbach, Piacentini, et al., 2015) is a 28-item self-report measure of the presence, frequency, and intensity of motor and vocal tics.

Premonitory Urge to Tic Scale (PUTS). The PUTS (Woods, Piacentini, Himle, and Chang (2005) is a 10-item self-report measure of the presence of intensity of premonitory urges to tic.

Yale-Brown Obsessive-Compulsive Scale (Y-BOCS). The Y-BOCS is the gold-standard clinician-rated measure of obsessive-compulsive disorder severity (Goodman, Price, Rasmussen, & Mazure, 1989a; 1989b).

Attention Deficit Hyperactivity Disorder (ADHD) Rating Scale. The ADHD Rating Scale is a 20-item scale derived from the ADHD criteria in DSM-5 (DuPaul, Power, Anastopoulos, & Reid, 2016).

Patient Health Questionnaire-9 (PHQ-9). The PHQ-9 is a widely-used 9-item self-report measure of depression (Kroenke, Spitzer, & Williams, 2001).

The Depression, Anxiety and Stress Scale (DASS). The DASS is a widely used 42-item self-report measure of depression, anxiety, and stress (Lovibond & Lovibond, 1995).

The Work and Social Adjustment Scale (WSAS). The WSAS (Mundt, Marks, Shear, & Greist, 2002) is a 5-item self-report measure of the degree of impaired functioning attributable to a specific syndrome/disorder.

Five Facet Mindfulness Questionnaire (FFMQ). The FFMQ (Baer, Smith, Hopkins, Krietemeyer, & Toney, 2006) is a widely-used 39-item self-report measure of five aspects of mindfulness: observing, describing, acting with awareness, non-judging of inner experience, and non-reactivity to inner experience.

Credibility and Expectancy Questionnaire (CEQ). The CEQ is a widely used 6-item self-report measure of the degree to which an individual finds their treatment credible and expects that it will lead to an improvement in their symptoms.

Patient Satisfaction Questionnaire (PSQ). The PSQ is an 8-item scale that assesses patients' satisfaction with treatment.

Self-Compassion Scale (SCS). The SCS is a 26-item self-report measure of levels of self-directed compassion (Neff, 2003).

Affective Reactivity Index (ARI). The ARI is a 7-item self-reported measure of irritability (Stringaris et al., 2012).

Brief Irritability Test (BITe). The BITe is a 5-item self-reported measure of irritability (Holtzman et al., 2015).

Tic Rating Form. A brief idiographic self-report rating of the severity of each participant's tics.

Problem Rating Form. A brief idiographic self-report rating of the severity of problems associated with tics.

Homework Adherence Form. A brief self-report assessment of the amount of home practice completed.

Adverse Event Monitoring Form. A brief self-report assessment of adverse events.

Treatment Questionnaire. A brief self-report assessment of other treatment received since completing study intervention.

Confidentiality

All information gathered about study participants will be kept strictly confidential. Participants will be assigned a confidential study ID which will be used to identify all online subject data and materials. The key linking participant names to the study ID will also be kept in a password protected file. Data will be stored on secure servers and/or in locked offices. Only study personnel will have access to study information. All videoconferences will be conducted via zoom.us, a secure, HIPAA compliant web-based videoconferencing platform.

We will also apply to the National Institute of Neurological Disorders and Stroke for a Certificate of Confidentiality for this study. We have included the recommended Certificate of Confidentiality statement in the attached consent form.

Because Massachusetts General Hospital is a HIPAA-covered entity, we have also included a privacy statement (drafted by MGH) in the consent form.

Because this is an online study, we will communicate with participants by email. We will inform all participants that we cannot guarantee the security of communications via email and that if they have questions or concerns that they do not want to share via email they should call study staff.

Audio recording

We will audio record the administration of the YGTSS at every assessment and 15% of assessments will be randomly selected for co-rating by [name] to ensure consistency in administration and determine inter-rater reliability. The audio recordings will be made by the IE on a digital voice recorder. The digital recordings will be labeled with the participant ID and saved to a password protected server at Massachusetts General Hospital. All digital recordings will be deleted following the completion of co-ratings.

Data Collection and Storage

Data will be collected via Qualtrics and housed on their secure server. For analysis, researchers will download study data from this server and save it in a password protected database on the Bowdoin server. All data collected on paper (phone screens, the SCID) will be stored in locked filing cabinets in secure offices.

Risks

It is possible that participants will experience mild emotional distress due to the personal nature of some of the questions. With the exception of questions necessary to determine eligibility, participants will be allowed to skip any questions that they do not feel comfortable answering.

It is also possible that participants will experience mild physical discomfort when completing the relaxation, mindful movement, or meditations. Participants will be instructed to engage in the practices at a level that feels comfortable for them.

It is also possible that participants will experience transient tic worsening when conversing with others with tics in the group videoconferences.

Meditation and supportive therapy can also be challenging and may make participants more aware of negative aspects of their lives. Additionally, although unlikely, intense meditation could cause or worsen symptoms in people who have certain psychiatric problems.

Adverse events will be assessed weekly. The PI (a licensed clinical psychologist with 10+ years of experience working with adults with tic disorders), will review and monitor all reported adverse events and determine, in consultation with [name], (a licensed clinical psychologist and the chief of psychology at Mass. General Hospital) what steps, if any, are needed to address the event. Additionally, participants will be encouraged to contact the PI via phone with any concerns.

Benefits

It is possible that participants will not directly benefit from this study. It is also possible that participants will experience a reduction in tic severity, intensity, or related impairment and/or positive changes in anxiety, mood, attention, irritability, or quality of life.

RESEARCH DESCRIPTION /INFORMED CONSENT

Participants will learn about the research through online advertisements, clinician referral, or word of mouth. Interested participants will then complete a phone screen and have the opportunity to ask questions about the research. Potentially eligible participants will then review the online consent form with the PI via phone or videoconference and have another opportunity to ask questions. Individuals who wish to participate in the study will be asked to electronically sign the consent form and return it to us via email prior to the screening assessment.

RESEARCH SITE(S)

This research will be conducted at Bowdoin College and Massachusetts General Hospital. Bowdoin College will serve as the central IRB for the study. Per Massachusetts General Hospital policy, after obtaining Bowdoin College approval, we will submit a central IRB application and copies of all Bowdoin-approved materials to the Mass. General Hospital/Partners Healthcare IRB for review.

SUBSEQUENT MODIFICATIONS

Eight modifications to the protocol were made subsequent to enrollment of the first participant. Four of these pertained to the addition or removal of study staff. Two pertained to the addition of new advertisements. One allowed for the inclusion of pregnant women (approval date 12/8/18). One added an assessment relevant to the COVID-19 pandemic (approval date 6/24/20).

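### Does one 6 h/week time figure for everyone, beside a comparator said to mirror MBIT in duration, hide an imbalance in assigned time that calls for a change?

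*Protocol*

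**What the plan says.** The Time Involvement paragraph of Section VII first counts the formal assessments: 2 h for screening and 1 h for each of four later visits. It then adds, for each participant, "approximately 6 hours per week for 8 weeks completing the intervention and self-report questionnaires". There is no split by arm.

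The content of that time is set out further on:

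- **Sessions, both arms** (Type of Involvement): "Both interventions will last 8 weeks and consist of eight weekly 90-minute therapist-facilitated group videoconferences".
- **Home practice, MBIT** (Interventions, MBIT): "All participants will also be asked to complete approximately 30 minutes/day 4-6x/week of home practice". Although this speaks of all participants, it stands in the MBIT description. The TICS description and footnote c of Table 1 confirm that it applies to MBIT only.
- **TICS** (Interventions, TICS): "The TICS condition will mirror the mindfulness-based tic reduction condition in format and duration". Later in the same paragraph: "Formal home practice will not be assigned".
- **Recording of practice**: the Homework Adherence Form is described as "A brief self-report assessment of the amount of home practice completed". Footnote c of Table 1 restricts it to MBIT because only that arm is given formal practice to do.

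The aim is stated as a comparison of two interventions: "We hypothesize that MBIT will result in significantly greater improvements in tic severity and tic-related impairment than TICS". The primary outcome is the YGTSS total tic score.

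**The concern.** Taken together, one weekly total for everyone and a comparator that mirrors MBIT in duration suggest arms matched on time. The components show they are not: MBIT participants are asked for more than twice the intervention hours of TICS participants. A reader who believed the arms were time-matched might credit a difference in tic score to the content of the mindfulness programme, when the programme also asked for 16 to 24 h more of participants' time.

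The recording of practice adds to the worry. TICS sessions may teach skills such as relaxation, which people can use at home without being asked, and nothing in Table 1 captures that. If no difference were found, unrecorded practice in TICS would be a possible explanation, and the data could not describe the real contrast in practice time.

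**Working it through.** **Is the 6 h figure reproducible?** The inputs are a 90-minute weekly session in both arms, 30 minutes of practice 4 to 6 times a week in MBIT, no assigned practice in TICS, and 8 weeks. Weekly intervention time is session hours plus assigned practice hours.

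| | MBIT | TICS |
|---|---|---|
| Session, h/week | 1.5 | 1.5 |
| Assigned practice, h/week | 0.5 × 4 = 2.0 to 0.5 × 6 = 3.0 | 0 |
| Intervention total, h/week | 3.5 to 4.5 | 1.5 |
| Over 8 weeks, h | 28 to 36 | 8 × 1.5 = 12 |
| Left for questionnaires if the total is 6 h/week | 6 − 4.5 = 1.5 to 6 − 3.5 = 2.5 | 6 − 1.5 = 4.5 |

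The ratio is 3.5/1.5 = 2.33 to 4.5/1.5 = 3.0. The gap is 2 to 3 h a week, or 16 to 24 h over 8 weeks. The questionnaires given to both arms do not alter the gap.

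**Can questionnaires fill the remainder?** In weeks 1 to 8, Table 1 lists the 10-item PUTS and three forms described as brief (tic rating, problem rating, adverse events). MBIT also has the brief homework form. The 39-item FFMQ is given once, at week 4, and the 6-item CEQ once, after week 3. The protocol gives no time for these. Assuming 0.25 to 1 h a week:

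- TICS: 1.75 to 2.5 h/week, so 6 h is 6/2.5 = 2.4 to 6/1.75 = 3.4 times the scheduled time.
- MBIT: 3.75 to 5.5 h/week, so 6 h is 6/5.5 = 1.1 to 6/3.75 = 1.6 times the scheduled time.

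The formal assessments cannot fill the gap, because the same sentence counts them separately. The neighbouring figures do add up: 2 + 4 × 1 = 6 h of assessments, and 8 × $10 + 4 × $30 = $200 of payment. The 6 h/week is therefore a generous rounding for the more demanding arm and does not fit TICS.

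**Is the mirror sentence contradicted?** The protocol spells out what the arms share: 8 weeks, eight sessions, 90 minutes each, a facilitated group by videoconference. On those elements the arms match exactly, with 8 × 1.5 = 12 h of therapist contact in each. The sentence would be wrong only if duration meant total assigned time, and the statement that TICS has no assigned practice, in the same paragraph, rules that reading out.

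**What depends on the figure?** The protocol attaches no outcome, comparison or decision to the 6 h/week. It stands beside the payment terms as an approximate statement of what taking part involves. Correcting it would leave the randomised comparison on the YGTSS total tic score as it is.

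**The case for a change.** The best case for acting has three parts. First, the hours conflict is real and needs no assumption, and correcting it would cost two sentences. That stands as a description: the single figure is wrong for TICS, and stating time by arm would be tidier. It is an editorial matter in a burden estimate, with no bearing on the trial's results.

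Second, a difference between arms cannot be separated from the extra assigned practice. This is true, but the protocol does not claim otherwise. Its question is how efficacious MBIT is compared with TICS, and home practice is written into MBIT. The protocol names mindfulness practice as a component of such interventions, so the added hours are reasonably read as part of the treatment under test. A caution against crediting content alone would guard against a claim the protocol never makes.

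Third, practice in TICS goes unrecorded, and one neutrally worded weekly item would capture it. The information would be of some interest. If MBIT participants completed 50% to 100% of their practice and TICS participants practised 0 to 1 h a week unasked (both assumed), the actual gap could lie anywhere from 8 × (0.5 × 2 − 1) = 0 h to 8 × 3 = 24 h. That range follows from the assumptions and says nothing about this trial. An adherence form has no obvious object where nothing is assigned, and footnote c gives that reason. Asking TICS participants each week about practice may also encourage it, which would alter the comparator. The protocol's list of later modifications shows that enrolment had already begun, so the item could reach only participants still in weeks 1 to 8, and the document does not say whether there are any.

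**Conclusion.** The arithmetic behind the concern is correct: 28 to 36 h of assigned intervention time in MBIT against 12 h in TICS, and a common 6 h/week that overstates TICS by a factor of about 2.4 to 3.4 if questionnaires take 0.25 to 1 h a week. That amounts to a loose burden estimate, a clerical matter. The mirror sentence holds for the sessions, and the asymmetry in home practice is disclosed where TICS is described and again under Table 1. Recording adherence only where practice is assigned is a reasoned choice. Adding a practice item in TICS would be a debatable trade-off with no effect on the primary comparison. The randomised comparison of MBIT with TICS answers the question the protocol asks, and no change to the plan is called for. This rests on reading that question as a comparison of whole interventions, as the protocol words it.

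### The adverse event form stops at Week 9 while outcomes run to Week 35; giving it at the two later visits is a cheap, low-priority improvement

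*Protocol*

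**What the plan says.** Table 1 of the protocol (Schedule of Assessments) marks the "Adverse Event Monitoring Form" in the columns for Weeks 1-8 and Week 9. The Week 13 and Week 35 cells are empty. The Assessment section describes the form as "A brief self-report assessment of adverse events" and describes no other adverse event instrument.

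The Risks section says "Adverse events will be assessed weekly", without giving an end date. It adds that the PI "will review and monitor all reported adverse events" and that "participants will be encouraged to contact the PI via phone with any concerns".

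At Weeks 13 and 35 the tic, global impression, psychiatric symptom and functioning measures continue. The Treatment Questionnaire, given only at those two visits, is "A brief self-report assessment of other treatment received since completing study intervention".

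**The concern.** Efficacy and solicited harms are followed for different lengths of time. A reader of the final report would see tic severity and 14 other listed instruments out to Week 35, but solicited adverse events only to Week 9. An arm-by-arm count of solicited events could not be extended past Week 9. Calls made at the participant's own initiative are not a good substitute, because willingness to report can differ between arms for reasons that have nothing to do with harm.

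The point belongs to the protocol rather than to an analysis plan. The visit schedule is fixed here, and data not collected at a visit cannot be recovered by analysis.

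**Working it through.** **1. Reading the table row.** The columns are Screening, Baseline, Weeks 1-8, Week 9, Week 13 and Week 35. The adverse event row reads blank, blank, X, X, blank, blank. The next row, the Treatment Questionnaire, has its two marks in the last two columns, as its description requires. The columns are therefore aligned, and the blanks are not an artefact of text extraction.

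**2. Does the table contradict the Risks section?** Time Involvement describes "approximately 6 hours per week for 8 weeks completing the intervention and self-report questionnaires". Payment gives $200 in total, $30 for each of four assessments, and $10 per week "for the weekly self-report questionnaires":

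- $200 − 4 × $30 = $80
- $80 ÷ $10 per week = 8 weeks

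Weekly self-report thus means the eight intervention weeks. Table 1 covers all eight and adds Week 9. Uncovered intervention weeks: 0 of 8. Text and table agree.

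**3. Length of the interval without the form.**

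- Week 9 to Week 13: 13 − 9 = 4 weeks
- Week 13 to Week 35: 35 − 13 = 22 weeks
- Total: 4 + 22 = 26 weeks, which is 26/35 = 74% of the time from baseline to the last visit
- Post-treatment visits without the form: 2 of 3

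**4. What is given at those visits.** Instruments marked at both Week 13 and Week 35: YGTSS, CGI-S, CGI-I, ATQ, PUTS, YBOCS, ADHD-RS, PHQ-9, DASS, WSAS, FFMQ, SCS, ARI, BITe and Treatment Questionnaire. That makes 15.

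**5. What the other routes catch after Week 9.**

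- *Worsening still present at the visit* in tics, obsessive-compulsive symptoms, ADHD symptoms, depression, anxiety, stress, irritability or functioning: caught by the repeated scales.
- *Events that led to treatment:* may surface in the Treatment Questionnaire, even if resolved by then.
- *Events already reported:* remain under PI monitoring, which has no stated end, although no follow-up question is scheduled.
- *Other psychiatric symptoms:* no listed instrument at these visits. The SCID is given at screening only.
- *Physical events:* no listed instrument is described as measuring them.
- *Untreated events that begin and end between visits:* known only if volunteered.

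The last three items are the actual gap.

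**6. Size of the change.**

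- Forms per participant now: 8 + 1 = 9; with the change: 9 + 2 = 11
- For 48 participants, all retained: 48 × 9 = 432 now and 48 × 11 = 528 with the change; 528 − 432 = 96 more, and 96/432 = 22%
- Listed instruments at each later visit: 16 instead of 15

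**The case against.** The strongest reply is that the window is a reasonable choice. In the Risks section, physical discomfort is tied to doing the exercises, and tic worsening is described as transient and tied to the group sessions. Both belong mainly to the intervention weeks. The Homework Adherence Form also ends at Week 9, so form and scheduled exposure finish together. The stated purpose is efficacy, and the protocol promises no adverse event comparison to Week 35. All of this stands, and it is why the point is a low-priority improvement and not a defect.

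It does not remove the point altogether. Visits are already being held, the instrument already exists, and the remaining routes leave the limited gap described in the working.

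Three readings should be resisted.

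- A reader might infer that the weekly statement in Risks conflicts with Table 1. The time and payment provisions show that it does not.
- A reader might infer that psychiatric worsening goes unmeasured after Week 9. The repeated scales measure much of it. The opposite inference, that they cover all of it, is not supported either: Risks speaks of certain psychiatric problems without naming them, and the scales measure only some symptom domains.
- A reader might take the 26 weeks as a measure of missed harm. It is calendar time after the intervention. The protocol gives no event rate, so the number of missed events cannot be estimated.

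**Conclusion.** The schedule is as described, and the point holds as a low-severity, inexpensive improvement. Solicited adverse event enquiry ends at Week 9 and outcome assessment at Week 35, so 2 of the 3 post-treatment visits lack the form. What is lost is limited to psychiatric or physical events outside the repeated scales, and untreated events that come and go between visits. The intervention period is fully covered, and the primary efficacy comparison is not touched.

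This rests on Table 1 and the text as posted. The form itself and the attached study schema are not shown. The COVID-19 assessment mentioned under Subsequent Modifications cannot be identified in Table 1, so 15 is the count of listed instruments and not necessarily everything given at those visits.

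**What to change.** Mark the existing form at Weeks 13 and 35 in both arms. Word it to cover the time since the previous assessment, and have it ask about the outcome of any event still open at Week 9. Report these answers separately from the weekly data, because recall runs over 4 and 22 weeks and not one. It would also help, as an editorial matter, to state the adverse event collection period in Risks.

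The cost is two more brief self-report forms per participant, at most 96 in all, plus some PI review time. Recall will be less reliable, above all over 22 weeks and for short-lived events.

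If the form is added during the trial, participants will have followed different schedules, so the report should say how many in each arm were asked at each visit. Subsequent Modifications records that an assessment was added after the first participant enrolled (approval date 6/24/20), so a route for such a change exists. For participants whose later visits have passed, no new data are needed: limit conclusions about solicited adverse events to Week 9 and say so.

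### Does scheduling the Tic Rating Form and Problem Rating Form only in Weeks 1-8 leave the trial without pre-to-post data that it needs?

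*Protocol*

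**What the plan says.** In the protocol's Assessment section, the Tic Rating Form is described in one sentence, "Tic Rating Form. A brief idiographic self-report rating of the severity of each" participant's tics, and its companion in another: "Problem Rating Form. A brief idiographic self-report rating of the severity of problems associated with tics". Neither sentence gives a time point, an outcome role or an analysis.

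In Table 1, the row for the "Problem Rating Form" and the row for the Tic Rating Form each hold a single mark, under Weeks 1-8. Footnotes a to c concern other instruments; footnote a, for example, says the "FFMQ will only be administered at week 4" (within the weekly column). Nothing limits the two rating forms to one week or adds a week outside treatment.

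On the primary outcome the YGTSS entry says: "The total tic score will serve as the primary outcome measure". For impairment, the WSAS "is a 5-item self-report measure of the degree of impaired functioning attributable to a specific syndrome/disorder". YGTSS, ATQ and WSAS are all marked at Weeks 0, 9, 13 and 35.

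Under Type of Involvement, the pre-intervention visit is set: "we will schedule baseline assessments via videoconference with the IE for the week prior to the initiation of the intervention". Under Payment, weekly questionnaires earn \$10 a week, and there is a separate \$30 "each for the baseline, post-treatment, one-month and 6-month follow-up assessments".

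**The concern.** The hypothesis is about improvement in tic severity and tic-related impairment. These two forms rate those two things for each person's own tics and problems, and no other listed measure is described as individualised. A baseline visit exists in the week before treatment, yet neither form is given there, nor at post-treatment or follow-up.

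If the trial relied on these forms for change, that would matter. The earliest reference would be the first weekly rating, and the protocol does not say whether it comes before or after session 1. Any change before that rating would be lost, and nothing after Week 8 could be described. Because the schedule fixes what is collected, a later analysis plan could not repair it.

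**Working it through.** **1. Is the schedule read correctly?** Yes. By column position in Table 1:

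| Measure | Week 0 | Weeks 1-8 | Week 9 | Week 13 | Week 35 |
|---|---|---|---|---|---|
| Tic Rating Form | no | yes | no | no | no |
| Problem Rating Form | no | yes | no | no | no |
| PUTS | yes | yes | yes | yes | yes |
| YGTSS, ATQ, WSAS | yes | no | yes | yes | yes |

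The Payment section agrees with eight weekly questionnaires and four assessments: 8 × \$10 + 4 × \$30 = \$80 + \$120 = \$200, the stated total.

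**2. Does the schedule conflict with anything?** No. The table sets weekly and assessment-visit use row by row: PUTS has both, the Homework Adherence and Adverse Event forms have Weeks 1-8 and Week 9, and the two rating forms have the weekly column only. Brief forms filled in weekly beside fuller instruments at the assessments is a coherent layout, and the separate payments match it. The protocol states no rationale, but nothing in it contradicts this one.

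**3. Does any stated aim need the missing ratings?** The hypothesis has two parts. Tic severity is covered by the YGTSS (primary) and the ATQ; impairment is covered by the WSAS. All have a baseline, a post-treatment and two follow-up values. Neither rating form is named as an outcome.

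**4. What can the forms still show?** Week 1 to Week 8 spans 7 of the 9 weeks between Week 0 and Week 9 (7/9 = 78%). None of the 35 − 9 = 26 weeks after Week 9 is covered. Within treatment, the arms are randomised, so their weekly levels and trajectories can be compared without a Week 0 value. A baseline covariate would add precision, but the comparison does not depend on it.

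**5. How much precision is at stake for weekly slopes?** This illustration assumes a linear trend; no correlation or variance below comes from the protocol. The sum of squared time deviations for n equally spaced weeks is n(n² − 1)/12:

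- Weeks 1-8: 8 × 63/12 = 42
- Weeks 0-9: 10 × 99/12 = 82.5

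Under constant correlation, adding Weeks 0 and 9 lowers within-person slope variance by 1 − 42/82.5 = 49%. Under first-order autoregressive correlation of 0.9 or 0.7, the variance ratios are 1.408 and 1.608, so the reductions are 1 − 1/1.408 = 29% and 1 − 1/1.608 = 38%.

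These figures leave out differences between people in their true slopes, which extra visits do not reduce. With residual variance 1 (independent errors) and between-person slope variance v, the reduction is 1 − (v + 1/82.5)/(v + 1/42):

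- v = 0.05: 1 − 0.0621/0.0738 = 16%
- v = 0.2: 1 − 0.2121/0.2238 = 5%

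The gain therefore runs from 5% to 49% over these assumptions, for a slope that is estimable either way.

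**The case for a change.** The strongest case for the concern is that these are the only individualised ratings in the trial and that adding them would be cheap. Two brief forms at Week 0 and Week 9 come to 2 × 2 × 48 = 192 extra completions for 48 participants, at visits that already take place. PUTS shows that a weekly self-report can also be given at every assessment. Ratings that were never taken cannot be supplied later.

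All of that is factually correct. It also stands that the timing of the first weekly form relative to session 1 is not stated. If it follows session 1, Week 1 is not a clean pre-treatment reference.

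None of this shows an error. A report of pre-to-post or lasting improvement on these forms would lack data, but the protocol announces no such report. Limiting claims on these forms to within-treatment change asks for nothing beyond what the protocol already implies. The order of form and session is a detail that operational documents may hold. Nor would a Week 0 rating be a pre-randomisation value, since Type of Involvement places random assignment after screening and before the baseline visit. Finally, the Subsequent Modifications section records a change approved on 6/24/20, after enrolment had begun, so Week 0 ratings could not be recovered for anyone already treated.

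**Conclusion.** The concern does not hold. The two forms do lack ratings at Weeks 0, 9, 13 and 35, but the protocol neither says nor implies otherwise and rests no conclusion on such ratings. The primary outcome and the hypothesis on severity and impairment are unaffected: the effect on them is nil. What is forgone is optional information on two supplementary weekly forms, plus some slope precision whose size depends wholly on assumed variances and correlations.

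This rests on the protocol alone and on the forms having no outcome role, as it stands there. If another trial document named either form as a pre-to-post or follow-up outcome, the question would need to be reopened.
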